Aim 2: Determine the feasibility of the efficacy study design. Feasibility will be assessed by examining the following outcomes related to recruitment, retention, and provider adherence: (1) number of participants approached for the study who are eligible and of those, the number who enroll in the study (i.e., agree to participate). Feasibility is defined as $\geq 50\%$ eligible and of these $\geq 30\%$ willing to participate in the proposed time frame. (2) participant completion of ACT-MI will be measured by the percentage of participants who complete treatment and receive an adequate dose (complete a minimum of 70% of the intervention). (3) percentage of participants lost to follow up (LTFU). The percentage of participants who fail to complete one- month and three-month follow-up visits will be measured, with $\leq 30\%$ LTFU considered feasible, informing

the necessary sample size and treatment retention strategies for future studies. (4) treatment fidelity checklists will examine provider adherence to treatment, with $\leq 15\%$ of deviations to be considered acceptable fidelity.

Aim 3: Select measures and calculate the necessary sample size for a future efficacy study.

Evaluate candidate measures based on the following factors: (1) Amount and distribution of missing data, (2) means and standard deviations, and (3) correlations with a measure of self-reported clinically significant change. Estimates of variability in outcome measures will inform power analysis and target sample size for a future efficacy study.

With the onset of the COVID-19 pandemic, it has become clear that the feasibility of delivering interventions through telehealth may be critical to their utility and that research methods must also be feasible for use through telehealth. Two aims related to conducting ACT-MI using telehealth are being evaluated:

Aim 4: Evaluate the acceptability of the ACT-MI intervention delivered over telehealth. ACT-MI will be delivered over telehealth as needed due to the COVID-19 pandemic. Acceptability of in person and telehealth data will be analyzed separately.

Aim 5: Evaluate the feasibility of the efficacy study design with all assessment sessions delivered over telehealth. ACT-MI and all assessment sessions will be delivered over telehealth as needed due to the COVID-19 pandemic. Feasibility of in person and telehealth data will be analyzed separately.

II. Background and Significance:

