Inclusion Criteria: 1) Eligible for VHA care (information obtained from review of medical record), 2) Age 18-89 (information obtained from review of medical record), 3) Has been deployed to a warzone (information obtained from Veteran self-report/screening interview), 4) Has experienced a morally injurious event which continues to interfere with functioning (information obtained from Moral Injury Events Scale [MIES], Moral Injury Questionnaire-Military Version [MIQ-M], and self-report/screening interview), and 5) Willing to be randomized and participate in either of the two conditions (information obtained from Veteran self-report/screening interview). 6) When groups are only being offered through videoconferencing, participants will need a computer/smartphone capable of accessing the VA approved videoconferencing platform in a private setting.

Exclusion Criteria: 1) Inability to demonstrate understanding of the postcard consent (as evidenced by inability to respond correctly to postcard consent questions or medical record review), 2) Inability to complete study measures (e.g., due to significant acute intoxication/withdrawal symptoms, mania, psychosis, aggression, catatonia, cognitive impairment) (results of veteran self-report, screening, or discretion of interviewer), 3) Imminent suicide risk (medical record or UWRAP), 4) Membership in a vulnerable population (e.g., pregnant women) (medical record or self-report), 5) History of significant violence towards VA staff (medical record), 6) Participation in another psychotherapy research study, (medical record

or self-report), and 7) Current participation in an EBP for a condition related to moral injury (medical record or self-report).

C. Study Design and Research Methods

Design: We are proposing a two arm, randomized, controlled pilot study to assess the feasibility of a future randomized clinical trial (RCT) evaluating the efficacy of ACT-MI. Candidate measures for a future efficacy trial will be administered at baseline, post-treatment, and one- and three-month follow-ups. Measures of acceptability will be administered following treatment completion/discontinuation. Veterans who are eligible to receive treatment at the VA ECHCS and who are eligible and interested in participating in the study will be enrolled and randomized to: (1) Present Centered Therapy (PCT-MI) or (2) ACT-MI.

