
receive up to eighteen hours of group psychotherapy across twelve group sessions. Prior to each treatment group, participants will complete process measures (PHLMS, AAQ-II, MEAQ-30 and CFQ-MI). On odd weeks participants will complete the AAQ-II and PHLMS and on even weeks participants will complete the MEAQ-30 and CFQ-MI. These will be assigned on odd and even weeks to minimize participant fatigue and to determine which measures might be most sensitive to change over time for use in a future efficacy trial. Groups will be randomly assigned to receive either the original measures or the measures with altered instructions (e.g., to identify experiences in the past week) so that we can better understand responding on these measures based on providing temporal instructions. At baseline and post-treatment for 7 days, 3 times per day, participants will complete EMA assessments. EMA will be structured to minimize its impact as a potential treatment procedure and instead will be explicitly designed to assess behavioral changes without necessarily prompting values driven behavior. ***Post-treatment Assessment***

Session. A study assessor will meet with participants in the ACT-MI and PCT-MI conditions and administer the treatment acceptability measures (CSQ-8, NEII, RT-C) and candidate outcome measures (VLQ, PROMIS, OQ-45, PHLMS, AAQ-II, AAQ-II past week MEAQ-30, MEAQ-30 past week, CFQ-MI, CFQ-MI past week, PHQ-9, PCL-5, E-MIS, AUDIT, BAM-R, ASIQ, and GC). **One-Month and Three-Month Follow-ups.** Participants will have the option to complete follow-up assessments via survey link (i.e., REDCap), mail, or phone/videoconferencing. In person follow-up appointments may still be offered, dependent on contact restrictions and recommendations related to the COVID pandemic. A different assessor, still blind to condition, will administer the one- and three-month follow-up measures (VLQ, PROMIS, OQ-45, PHLMS, AAQ-II, AAQ-II past week MEAQ-30, MEAQ-30 past week, CFQ-MI, CFQ-MI past week, PHQ-9, PCL-5, E-MIS, AUDIT, BAM-R, ASIQ, GC, and CSQ).

Recruitment:

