Aim 2: Determine the feasibility of the efficacy study design. Feasibility will be assessed by examining the following outcomes related to recruitment, retention, and provider adherence **a) Participant recruitment rates.** The number of participants approached for the study who are eligible to participate and of those, the number who enroll in the study (i.e., willingness to participate) will be evaluated. Feasibility will be defined as $\geq 50\%$ eligible and of these $\geq 30\%$ willing to participate in the proposed time frame. **b) Participant Retention.** Participant completion of ACT-MI will be measured by the percentage of participants who complete treatment and receive an adequate dose (completed a minimum of 70% of the intervention). Reasons for termination will be examined via the RT-C/T. The percentage of participants lost to follow up (LTFU) will be calculated as the percentage of participants who fail to complete one-month and three-month follow-up visits, with $\leq 30\%$ LTFU considered feasible. This will inform the necessary sample size and treatment retention strategies for future studies. **c) Provider adherence.** To examine the extent to which ACT-MI can be delivered as intended ($\leq 15\%$ of deviations for each clinician across participants on the treatment fidelity checklist), the proportion of sessions in which each clinician achieved acceptable fidelity out of all of the clinician’s sessions will be reported for all study clinicians. Qualitative review of fidelity checklists will be used if treatment fidelity is less than desired and areas of difficulty will be identified to inform training procedures for clinicians and treatment manual revisions.

Aim 3: Select measures and calculate necessary sample size for a future efficacy study. Evaluate candidate measures based on the following factors: (1) Amount of missing data and its distribution for all measures across groups; (2) means, standard deviations, and 95% confidence

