intervals for all measures within and across groups; and (3) correlations and 95% confidence intervals between a self-reported clinically significant change measure and candidate measures across groups. Missing data and frequency distributions will be examined to identify measures that have the least amount of missing data, and the extent of outliers or other anomalies. Means and standard deviations will be examined to identify and exclude measures with limited sensitivity to change due to ceiling or floor effects, or restriction of range.⁷⁷ Finally, higher correlations between participants' scores on the Global Ratings of Change Scale and the candidate measures will suggest that these measures are more sensitive to clinically significant change. Confidence intervals will be examined to determine how much to emphasize these findings when selecting measures. The study team will work closely with [name] in considering these various statistics and their limitations when selecting the most promising outcome and mediational measures for the future efficacy study.

After the primary outcome measure has been selected, we will calculate the necessary sample size for the efficacy study. This will require an estimate of variability and effect size in the target sample. We will estimate variability across groups at baseline and the variability of change scores on the outcome measure. The estimate with the greatest variability will be used in our power calculation because it will provide the most conservative (i.e., largest) estimate of the necessary sample size. Unlike estimates of variability that can be based on the entire sample, estimates of effect sizes are limited by the group sizes. Increasingly, methodological experts argue against the use of pilot data to estimate effect sizes because of limitations related to sample size and protocol/intervention changes, leading to invalid estimates. Instead, best practice is to set the effect size in power calculations to whatever value is considered minimally clinically significant.¹⁷ We will use the available literature and consultation with experts on measures of functioning when selecting this effect size and calculating the necessary sample size for the efficacy study.⁶⁷

Aim 4 and Aim 5: The analyses described above for Aim 1 and Aim 2 will be replicated using data collected from Veterans who participated in the intervention and study remotely (i.e., using videoconferencing and REDCap).

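### Aims 4 and 5 define the telehealth analysis set by remote participation, so the telehealth recruitment criteria are met by construction and randomised never-starters drop out of the retention figures

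*Combined protocol and SAP*

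**What the plan says.** Section I (Aims 4 and 5) adds two telehealth objectives. For Aim 5 it states: "Feasibility of in person and telehealth data will be analyzed separately". A parallel sentence covers acceptability under Aim 4. Neither gives a denominator or a rule for assigning a Veteran to a mode.

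The only analysis set is in section VII, Aim 4 and Aim 5: the Aim 1 and Aim 2 analyses "will be replicated using data collected from Veterans who participated in the intervention and study remotely". Remote is explained there as use of videoconferencing and REDCap.

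The analyses to be repeated include Aim 2a, recruitment: "The number of participants approached for the study who are eligible to participate and of those, the number who enroll in the study". The criteria are at least 50% eligible and, of these, at least 30% willing. Aim 2b adds the percentage who complete treatment (at least 70% of the intervention, with no pass mark for that percentage) and loss to follow-up, where at most 30% counts as feasible.

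Three other places bear on mode:

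- Inclusion criterion 6 (section IV.B): "When groups are only being offered through videoconferencing, participants will need a computer/smartphone", and a private setting to use it in.
- Baseline and treatment (section IV.C, Procedures): baseline is in person where possible, and groups go to video when necessary. Randomisation takes place at the end of the baseline session, and the wait for treatment depends on group start dates.
- Follow-up (same section): "Participants will have the option to complete follow-up assessments via survey link (i.e., REDCap), mail, or phone/videoconferencing". In-person follow-up may still be offered.

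**The concern.** A recruitment rate needs people in its denominator who did not enrol. The sentence for Aims 4 and 5 admits only people who took part, so it cannot yield the rates that Aim 5 borrows from Aim 2. The barrier most specific to telehealth, lack of a suitable device or a private place, acts at screening. It is therefore invisible in this set.

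The set also depends on something that happens after randomisation, namely whether the Veteran took part in the intervention remotely. Someone randomised who never attends a remote group is outside it, yet is a treatment non-completer.

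Finally, mode can differ between baseline, treatment and follow-up within one participant, and nothing says where such a participant belongs.

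The pilot exists to settle the design of an efficacy trial. A telehealth recruitment criterion that cannot fail tells that trial nothing about whether telehealth recruitment works.

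**Working it through.** **The plan's own figures.** The only stated sample-size figure is 2 × 36 = 72 participants (section VII, Sample Size). It reproduces and is not in dispute. The documents give no telehealth counts, so every count below is an assumption used to show direction and scale.

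**Step 1: recruitment.** Let A be the number approached, E the number eligible and N the number enrolled. Aim 2a needs E/A ≥ 50% and N/E ≥ 30%. In a set made up only of remote participants, A = E = N, so both ratios equal 1 whatever happened at screening.

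- True rates exactly at the limits, with 36 remote enrolees assumed: E = 36/0.30 = 120 and A = 120/0.50 = 240. The set sees 36/36 and 36/36.
- True rates below the limits, with 100 approached, 40 eligible and 10 enrolled assumed: 40/100 = 40% and 10/40 = 25%, so both criteria fail. In the set, assuming all 10 take part remotely, they are 10/10 and 10/10, and both pass.

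Veterans who fail criterion 6 belong in A but not in E. In the set they are in neither.

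**Step 2: treatment completion.** Assume 36 Veterans randomised to remote groups, of whom 4 never start, leaving 32 starters. If 8 starters do not complete, non-completion is 8/32 = 25.0% in the set and (8 + 4)/36 = 33.3% of all randomised. Never-starters are always non-completers, so this difference has one direction. It is zero if everyone starts.

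**Step 3: loss to follow-up.** Take the same 36 and 4, and assume 8 of the 32 starters are lost.

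| Never-starters lost | Set (starters only) | All randomised |
|---|---|---|
| 4 of 4 | 8/32 = 25.0% | 12/36 = 33.3% |
| 1 of 4 | 8/32 = 25.0% | 9/36 = 25.0% |
| 0 of 4 | 8/32 = 25.0% | 8/36 = 22.2% |

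The set understates loss only if never-starters are lost more often than starters.

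Suppose all never-starters are lost. With loss d among starters and a never-start share s, the all-randomised rate is d(1 − s) + s. It reaches 30% when s = (0.30 − d)/(1 − d):

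- d = 15%: s = 0.15/0.85 = 17.6%
- d = 20%: s = 0.10/0.80 = 12.5%
- d = 25%: s = 0.05/0.75 = 6.7%

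**Step 4: mixed modes.** The sentence requires both the intervention and the study to be remote. A participant treated by video who had an in-person baseline, or who returns follow-up by mail or in person, meets the first condition and only partly the second. No rule places this participant in either mode.

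**The case against.** The best defence is that "The analyses described above for Aim 1 and Aim 2 will be replicated" carries the approached and eligible denominators across to telehealth, and that the protocol uses the word participants loosely; Aim 2a itself applies it to people merely approached. On that reading a Veteran who fails criterion 6 counts as approached and ineligible. This may well be what the authors intend, but it contradicts the restriction in the same sentence. It also cannot be carried out as things stand, because nothing assigns a Veteran who did not enrol to a mode. Preliminary screening is in person or by telephone for everyone, so the screening channel does not settle it.

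The defence is right on retention. A reader might infer that telehealth dropout and loss to follow-up are understated outright, or that the set holds only those who stayed. The wording asks for participation, not completion. A Veteran who attends a remote session and then stops remains in the set, and those who withdraw from treatment can stay in the study. Only never-starters are clearly removed, and their effect on loss to follow-up can go either way.

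A reader might also infer that an in-person participant who picks a remote follow-up channel moves into the telehealth set. The sentence requires remote intervention as well, so that participant stays outside.

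Missing satisfaction scores under Aim 1 affect both modes and are not created by this sentence.

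**Conclusion.** Wrong as written, and it should be changed. The recruitment part follows from the wording alone: both telehealth rates are 100% by construction, and criterion 6 exclusions never count. It fails only if the sentence is read against its own restriction.

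The retention part is conditional. Non-completion is understated if any Veteran randomised to a remote group never starts. Loss to follow-up may be understated, unchanged or overstated. On the assumed counts the set gives 25.0%, against 22.2% to 33.3% of all randomised, a range that crosses the 30% limit. The documents give neither the number of never-starters nor their follow-up, so a firm claim of understated loss is not supported.

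The analyses are descriptive and no efficacy test or safety rule is involved. What is affected is the information that Aims 4 and 5 are meant to provide.

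**What to change.** Replace the sentence for Aims 4 and 5 with a classification by the mode that the study offered:

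- **Recruitment (Aim 2a).** Classify every approached Veteran by the mode on offer at first screening contact. Use all approached and all eligible in that mode as denominators, and count criterion 6 exclusions as telehealth ineligibles. State in advance where a Veteran goes if both modes are on offer.
- **Completion, loss to follow-up and satisfaction.** Use all randomised participants for completion and loss to follow-up. For these two and the satisfaction proportion, classify each participant by the planned delivery mode of the assigned group at its first session, whatever channel is used for assessments. If the group never starts, or the participant never attends, use the mode planned at randomisation.
- **Groups that change mode part-way.** Keep them in their first-session category for the main figures, and show them separately as a descriptive sensitivity display.

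The change is confined to the analysis and takes a few sentences. Aim 2a already requires counts of those approached and eligible. What is added is the mode on offer at first contact; the documents do not say whether this is recorded, so it may have to be derived from dates. The cost is a little more tabulation and telehealth figures that may be less favourable. A Veteran may also be classed differently for recruitment and retention if the mode on offer changes before the group starts; a footnote with the number affected would cover this.

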Appendix 1 Safety Monitoring Plan

UWRAP Protocol Guidelines, Decision Rules and Follow-up Procedures

Part I: Pre-risk Assessment of Suicidal Risk

Step 1: Using the Face Sheet, assess subject's mood and suicidality before administering measures or beginning an intervention

On a scale of 1 to 7:

- *what is your level of stress right now?*
- *what is your urge to harm yourself now?*
- *what is your intent to kill yourself right now?*
- *what is your urge to use drugs or alcohol right now?*

Step 2: Identify level of suicide risk

Examine participants' responses to suicide specific questions

- *what is your urge to harm yourself now?*
- *what is your intent to kill yourself right now?*

Step 3: Determine if further risk assessment is warranted

3a. If scores are greater than one, but less than or equal to 4 on either of the two suicide items, yet there are no apparent signs of distress or immediate concerns, continue with the research protocol and utilize the following strategies if needed:

- Pace the sessions**
- Check in with participant to see how they are doing**
- Allow more frequent breaks if needed**

3b. If participants' scores are greater than a 4 on either of the two suicide items

OR

Scores are equal to or less than 4 on either of the two suicide items, but participant appears distressed or exhibits other suicide signs or symptoms

Contact designated clinician to further evaluate risk

Step 4: Conduct further risk assessment if warranted

If indicated in step 3 above, the designated clinician will complete the Suicide Risk Assessment Worksheet (pg. 6-7 of the UWRAP)

Step 5: Initiate the appropriate follow up actions

Based on participant's responses on the suicide risk assessment worksheet, the designated clinician will initiate the appropriate follow up procedures. This may include:

- Referring the participant to the mental health clinic if not in treatment,
- Encouraging participant to check in with his/her mental health, primary care provider, or other health provider
- Walking the participant to urgent care (including Psychiatric Emergency Services) if risk is imminent or contacting 911.
- Continuing with the research protocol and utilizing the following strategies:
Pace the sessions

Check in with participant to see how they are doing
Allow more frequent breaks if needed

Part II: Debriefing Protocol Suicidal Risk

Step 1: Using the Debriefing Protocol, assess subject's mood and suicidality following administration of study measures

On a scale of 1 to 7:

.....*what is your level of stress right now?*
.....*what is your urge to harm yourself now?*
.....*what is your intent to kill yourself right now?*
.....*what is your urge to use drugs or alcohol right now?*

Step 2: Identify level of suicide risk

Examine participants' responses to suicide specific questions

.....*what is your urge to harm yourself now?*
.....*what is your intent to kill yourself right now?*

***Note changes, and in particular, increase in suicidality from the pre-assessment risk**

Step 3: Determine if further risk assessment is warranted

3a. If scores are greater than one, but less than or equal to 4 on either of the two suicide items, yet there are no apparent signs of distress or immediate concerns

Encourage them to contact their mental health or primary care provider if needed

3b. If participants' score is greater than a 4 on either of the two suicide items **OR**

Scores are equal to or less than 4 on either of the two suicide items, but participant reports at least a two points increase since the pre-risk assessment, or appears distressed and exhibits other suicide signs or symptoms

Contact the designated clinician to further evaluate risk

Step 4: Conduct further risk assessment if warranted

If indicated in step 3b above, the designated clinician will complete the Suicide risk assessment worksheet (pg. 6-7 of the UWRAP)

Step 5: Initiate the appropriate follow up actions

Based on participant's responses on the suicide risk assessment worksheet, the designated clinician will initiate the appropriate follow up procedures. This may include:

- Referral to the MH clinic if not in treatment,
- Encouraging participant to check in with his/her mental health, primary care provider, or other health provider
- Walking the participant to urgent care (including Psychiatric Emergency Services) if risk is imminent or calling 911.
- Providing the participant with the VA national crisis hotline number
